Amendment 01	03-Jun-2013	
This amendment serves to revise the design of the study from a randomized, active controlled parallel group design to a single arm design by removing the enoxaparin arm.
 
Incorporate other minor changes to correct and/or clarify protocol requirements
 
In addition there are editorial changes throughout the document due to adaptation of the previous protocol version to the new BMS Protocol Template
 
This revision applies to all subjects and will serves in lieu of the original protocol.

Original Protocol	12-Nov-2012	Not applicable

SYNOPSIS

Clinical Protocol CV185158

Title of Study: Protocol CV185158: A Phase IV, Open-Label, Multi-center Study to Evaluate the Safety of Apixaban in Indian Subjects Undergoing Elective Total Knee Replacement or Total Hip Replacement Surgery

Investigational Product(s), Dose and Mode of Administration, Duration of Treatment with Investigational Product(s): Subjects will receive oral apixaban, 2.5 mg twice daily for 12 ± 2 days in subjects undergoing TKR or 35 ± 2 days in subjects undergoing THR.

Study Phase: 4

Research Hypothesis: Apixaban 2.5 mg BID is well-tolerated for venous thromboembolism (VTE) prophylaxis in Indian subjects undergoing total hip or knee replacement.

Primary Objective: Evaluate the safety of apixaban in prophylaxis of VTE in Indian patients undergoing elective total knee or hip replacement.

Study Design: Open-label with endpoint adjudication. Subjects with planned surgery for total knee replacement (TKR) or total hip replacement (THR) will be screened for inclusion up to 14 days before surgery. Subjects will receive oral apixaban, 2.5 mg twice daily, with the first dose administered 12-24 hr after surgery, and continuing for 12 ± 2 days in subjects undergoing TKR or 35 ± 2 days in subjects undergoing THR.

During hospitalization, subjects will be observed for signs or symptoms of venous thromboembolism or bleeding. After hospital discharge, subjects will be instructed to contact the investigator for adverse events including signs or symptoms of bleeding, deep vein thrombosis (DVT) or pulmonary embolism (PE). At the end of the intended treatment period and at the end of the 30-day follow-up period, the patients will come to attend an in person visit or a phone visit if an in person visit is not planned.

SCREENING PERIOD (up to 14 days prior to surgery)

Subjects undergoing total hip replacement or total knee replacement surgery (including revisions) without known or suspected hereditary or acquired bleeding or coagulation disorders who meet the inclusion/exclusion criteria are eligible. Screening clinical laboratory samples will be collected during this period.

↓

ENROLLMENT (from 4 days before surgery to 24 hours after surgery)

Eligible subjects (N = 500) will be assigned to apixaban 2.5 mg PO starting 12 - 24 hours after completing skin wound closure, then BID for 35 ± 2 days for the subjects undergoing total hip replacement or 12 ± 2 days for the subjects undergoing total knee replacement. Sites will call into the IVRS system to record whether the subject's planned surgery is a hip replacement or knee replacement.

↓

TREATMENT PERIOD (35 days \pm 2 days for THR subjects or 12days \pm 2 for TKR)

Treatment Period Visits: Day 1 (day of surgery), Day 2, Day 7 \pm 2, Day 12 \pm 2 for TKR or Day 35 \pm 2 for THR patients. The Day 7, 12 or 35 visit should ideally be an in-person visit. If this is not possible, a telephone follow-up visit will be performed.

While hospitalized, subjects will be evaluated daily for symptomatic VTE (DVT and/or PE) and bleeding events. After hospital discharge, subjects will report all AEs including, but not limited to, signs and/or symptoms suggestive of DVT or PE and bleeding, to the Investigator.

↓

FOLLOW-UP PERIOD (30 days after last dose of study drug)

Follow-up Visits: The follow up visit will occur 30 days after the last dose of study drug. TKR subjects will have their follow-up visit at Day 42 ± 2 days and THR subjects will have their follow up visit at Day 65 ± 2 days. The follow-up visit should ideally be an in-person visit. If this is not possible, a telephone follow-up visit will be performed.

Subjects will report all AEs, including those signs and/or symptoms suggestive of DVT and/or PE and bleeding, to the Investigator.

Study Population: Subjects Undergoing Elective Total Knee Replacement or Total Hip Replacement Surgery

Main Inclusion Criteria:

Male or female subjects over the age of 18, who are scheduled for elective total knee or hip replacement or a revision of at least one component of a total knee or hip replacement. Subjects must be willing and able to give written informed consent prior to any screening procedures.

Women of childbearing potential (WOCBP) must be using an adequate method of contraception to avoid pregnancy throughout the treatment period of the study in such a manner that the risk of pregnancy is minimized.

Main Exclusion Criteria:

WOCBP who are unwilling or unable to use an acceptable method to avoid pregnancy for the entire treatment period of the study

Women who are pregnant or breastfeeding

Known or suspected, acquired or bleeding or coagulation disorder in the subject or a first degree relative

Known coagulopathy

Active bleeding or at high risk for bleeding

Brain, spinal, ophthalmologic, or major surgery or trauma within the past 90 days

Active hepatobiliary disease

Two consecutive blood pressure readings within 15-30 minutes with supine SBP > 180 mm Hg or supine DBP > 105 mm Hg

Hemoglobin < 9 g/dL & Platelet count < 100,000/mm³

Creatinine clearance < 30 mL/min as estimated by the method of Cockcroft and Gault

Active hepatobiliary disease, based on an ALT or AST > 2xULN or a Total Bilirubin ≥ 1.5xULN (unless an alternative causative factor [eg, Gilbert's syndrome] is identified)

Any antiplatelet agents (including clopidogrel) other than aspirin

Vitamin K antagonist or other novel oral anticoagulant (such as rivaroxaban or dabigatran)

Ongoing unfractionated heparin or low molecular weight heparin use

Use of thrombolytics within past 7 days.

Study Assessments and Primary Endpoint: The primary endpoint is the incidence of adjudicated major or clinically relevant nonmajor bleeding. Secondary endpoints include adjudicated DVT or PE and all-cause death. These primary and secondary endpoints will be assessed up to end of treatment + 2 days.

Statistical Methods: The primary objective of the study is to evaluate the safety of apixaban in prophylaxis of VTE in Indian patients undergoing elective total knee or hip replacement. The primary study endpoint is a composite of International Society on Thrombosis and Haemostasis (ISTH) major bleeding/clinically relevant non-major bleeding (CRNM) in subjects undergoing elective total knee or hip replacement at the end of treatment + 2 days.

Total of 500 subjects will be enrolled and allocated to apixaban. The sample size of the study is determined by requirement of regulatory agency rather than statistical considerations. With 500 subjects and event rate of 4.36% for ISTH major or clinically relevant non-major bleeding, the width of the 95% CI for the event rate will be (2.6%, 6.2%) and width of the CI is 3.6%.

Subgroup analyses by surgery type will also be conducted.

TABLE OF CONTENTS

TITLE PAGE	1
DOCUMENT HISTORY	3
SYNOPSIS.....	4
TABLE OF CONTENTS.....	7
1 [REDACTED].....	9
[REDACTED].....	9
[REDACTED].....	9
[REDACTED].....	9
[REDACTED].....	10
[REDACTED].....	10
2 ETHICAL CONSIDERATIONS.....	10
2.1 Good Clinical Practice	10
2.2 Institutional Review Board/Independent Ethics Committee.....	10
2.3 Informed Consent.....	11
3 INVESTIGATIONAL PLAN.....	12
3.1 Study Design and Duration.....	12
3.1.1 Screening.....	13
3.1.2 Enrollment.....	13
3.1.3 Treatment Period.....	13
3.1.4 Follow-up Period.....	14
3.2 Post Study Access to Therapy.....	14
3.3 Study Population.....	14
3.3.1 Inclusion Criteria.....	14
3.3.2 Exclusion Criteria.....	15
3.3.3 Women of Childbearing Potential	16
3.4 Concomitant Treatments.....	17
3.4.1 Prohibited and/or Restricted Treatments.....	17
3.4.2 Other Restrictions and Precautions.....	17
4 TREATMENTS	19
4.1 Study Treatments	20
4.1.1 Investigational Product.....	21
4.1.2 Noninvestigational Product	21
4.1.3 Handling and Dispensing	21
4.2 Method of Assigning Subject Identification	21
4.3 Selection and Timing of Dose for Each Subject.....	22
4.4 Blinding/Unblinding	22
4.5 Treatment Compliance.....	22
4.6 Destruction and Return of Study Drug	22
4.6.1 Destruction of Study Drug	22
4.6.2 Return of Study Drug	22
5 STUDY ASSESSMENTS AND PROCEDURES.....	23
5.1 Flow Chart/Time and Events Schedule.....	23
5.2 Study Materials	27
5.3 Safety Assessments.....	27

5.4 Efficacy Assessments.....	28
5.4.1 Primary Efficacy Assessment.....	29
5.4.2 Secondary Efficacy Assessments.....	29
[REDACTED].....	29
6 ADVERSE EVENTS.....	29
6.1 Serious Adverse Events	29
6.1.1 Serious Adverse Event Collection and Reporting.....	30
6.2 Nonserious Adverse Events	31
6.2.1 Nonserious Adverse Event Collection and Reporting.....	31
6.3 Laboratory Test Abnormalities.....	31
6.4 Pregnancy.....	32
6.5 Overdose	32
6.6 Potential Drug Induced Liver Injury (DILI).....	32
6.7 Other Safety Considerations	33
7 DATA MONITORING COMMITTEE AND OTHER EXTERNAL COMMITTEES	33
7.1 Data Monitoring Committee.....	33

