3.1.3 Treatment Period

The day of surgery is Day 1.

The first dose of apixaban will be administered 12 - 24 hours after completing skin wound closure, typically in the morning of Day 2 and then BID for 35 ± 2 days for the subjects undergoing total hip replacement or 12 ± 2 days for the subjects undergoing total knee replacement.

While hospitalized, subjects will be evaluated on Day 1, Day 2 and discharge day for suspected symptomatic VTE, bleeding events or any AEs or SAEs.

At any subsequent treatment visits (Day 7 ± 2 and Day 12 ± 2 for TKR subjects or Day 7 ± 2 and Day 35 ± 2 for THR subjects), subjects will be instructed to report to the investigator all AEs, including signs and/or symptoms suggestive of VTE and any bleeding events they experienced since their last visit. Subjects with signs and/or symptoms of VTE at any time should return to the hospital/clinic and undergo appropriate diagnostic evaluation.

If study medication is discontinued for a suspected DVT and or PE, alternative antithrombotic prophylaxis may be initiated per the Investigator's discretion and standard of care. Every effort

must be made to confirm a suspected DVT and/or PE diagnosis before discontinuing study medication and initiating treatment per the Investigator's standard of care.

Samples for laboratory assessment of hematology will be obtained on the day of discharge.

Urine pregnancy test will be performed on Day 12 for TKR subjects and on Day 35 for THR subjects.

Dosing Diaries should be collected at Day 7 & Day 12 for TKR subjects and at Day 7 & Day 35 for THR subjects.

Subjects should be encouraged to return for an in person visit on Day 7 and Day 12 for TKR and Day 7 and Day 35 for THR. Alternatively those visits would be performed by phone.

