3.1.4 Follow-up Period

As appropriate and per the Investigator's discretion and standard of care, alternative antithrombotic prophylaxis may be initiated the day after the last dose of study medication.

For subjects undergoing TKR surgery, follow-up study visit will occur on Day 42 ± 2 and for subjects undergoing THR surgery, the follow up visit will occur on Day 65 ± 2. Subjects should be encouraged to return for an in person follow up visit at Day 42 (TKR) or Day 65 (THR). Alternatively those visits would be performed by phone.

Subjects will be asked to report to the Investigator, all AEs/SAEs including those symptoms suggestive of DVT and/or PE and bleeding. Suspected DVT and/or PE will be evaluated using the appropriate diagnostic assessment.

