4.3 Selection and Timing of Dose for Each Subject

Study medication for this study is defined as apixaban 2.5 mg tablets. Subjects will receive apixaban tablets.

- The first oral dose will be given 12 - 24 hours after completing skin wound closure, typically in the morning of Day 2, followed by BID dosing for 12 ± 2 days in subjects undergoing TKR or 35 ± 2 days in subjects undergoing THR.
- Study subjects will take one tablet in the morning and one tablet in the evening.

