- admission encountered for another life circumstance that carries no bearing on health status and requires no medical/surgical intervention (eg, lack of housing, economic inadequacy, care-giver respite, family circumstances, administrative).

6.1.1 *Serious Adverse Event Collection and Reporting*

Following the subject's written consent to participate in the study, all SAEs, whether related or not related to study drug, must be collected, including those thought to be associated with protocol-specified procedures. All SAEs must be collected that occur during the screening period and within 30 days of discontinuation of dosing. The investigator should report any SAE occurring after these time periods that is believed to be related to study drug or protocol-specified procedure.

An SAE report should be completed for any event where doubt exists regarding its status of seriousness.

If the investigator believes that an SAE is not related to the study drug, but is potentially related to the conditions of the study (such as withdrawal of previous therapy, or a complication of a study procedure), the relationship should be specified in the narrative section of the SAE Report Form.

SAEs, whether related or not related to study drug, and pregnancies must be reported to BMS (or designee) within 24 hours. SAEs must be recorded on the SAE Report Form; pregnancies on a Pregnancy Surveillance Form (electronic or paper forms). When using paper forms, the reports are to be transmitted via email or confirmed facsimile (fax) transmission to:

SAE Email Address: See Contact Information list.

SAE Facsimile Number: See Contact Information list.

For studies capturing SAEs/pregnancies through electronic data capture (EDC), electronic submission is the required method for reporting. The paper forms should be used and submitted immediately, only in the event the electronic system is unavailable for transmission. When paper forms are used, the original paper forms are to remain on site.

SAE Telephone Contact (required for SAE and pregnancy reporting): See Contact Information list.

If only limited information is initially available, follow-up reports are required. (Note: Follow-up SAE reports should include the same investigator term(s) initially reported.)

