## 6 STUDY PERIODS, TREATMENT REGIMENS AND POPULATIONS FOR ANALYSES

### 6.1 Study Periods

In all listings, summaries and statistical analyses, the term '**Intended Treatment Period**' refers to the period that starts with the enrollment.

In all listings, summaries and statistical analyses, the term '**Treatment Period**' will refer to the period between the first administration of study medication (post-surgery oral apixaban) and 2 days after the last administration of study medication (end of treatment). This period will be the basis for the summaries of safety and efficacy.

In all listings, summaries and statistical analyses, the term "**Follow-up Period**" will refer to the period starting after the "Treatment Period" ended through 30 days after discontinuation of study drug (for treated subjects).

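### The fixed Day 42/65 ± 2 follow-up visit does not guarantee the stated 30 days from last dose, so the last scheduled safety contact can come a few days early

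*Protocol*

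**What the plan says.** The follow-up part of the synopsis gives two timing rules one after the other. The first is relative to treatment: "The follow up visit will occur 30 days after the last dose of study drug". The second is by study day: "TKR subjects will have their follow-up visit at Day 42 ± 2 days". The hip counterpart is Day 65, with the same allowance.

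Elsewhere the two rules separate.

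- **Fixed days only:** protocol 3.1.4 (Follow-up Period), 3.4.2 (visits after premature discontinuation) and Tables 5.1-1 and 5.1-2. The tables schedule no AE/SAE assessment after this visit.
- **30 days from last dose only:** protocol 3.1 (a 30-day follow-up period beginning the day after the last dose), protocol 6.1.1 ("All SAEs must be collected that occur during the screening period and within 30 days of discontinuation of dosing") and SAP 6.1 (the Follow-up Period ends 30 days after study drug stops).

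The day count is set in protocol 3.1.3: "The day of surgery is Day 1". Sections 3.1.3 and 4.3 put the first dose 12 to 24 hours after wound closure, which they expect to be Day 2 as a rule. Section 4.3 then sets the length of treatment: "followed by BID dosing for 12 ± 2 days in subjects undergoing TKR or 35 ± 2 days in subjects undergoing THR". No passage says which rule prevails when they give different dates.

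**The concern.** The study day of the last dose varies, because dosing length has its own ± 2 day allowance and the count starts from surgery, not from first dose. A visit fixed by study day therefore does not keep a constant distance from the last dose. A site working from 3.1.4 and the schedule tables could make its last planned contact before the 30-day window has closed.

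At stake is the completeness of AE and SAE data at the end of follow-up. SAP 7.6 summarises AE incidence for the follow-up period, and SAP 6.1 runs that period to 30 days after discontinuation. A subject last contacted on day 26 would be summarised as if asked about all 30 days, and the SAP does not flag this.

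**Working it through.** **Inputs.** Surgery is Day 1 (protocol 3.1.3). First dose is typically Day 2 (3.1.3, 4.3). Dosing lasts 10 to 14 days for TKR and 33 to 37 days for THR (4.3). The visit falls on Day 40 to 44 or Day 63 to 67 (synopsis, 3.1.4, tables).

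**The plan's own figures.** 12 + 30 = 42 and 35 + 30 = 65. These are exact when the last dose falls on Day 12 or Day 35.

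**Formulas.** Last-dose day = first-dose day + length − 1. Gap = visit day − last-dose day.

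**Typical Day 2 start.**

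| | TKR | THR |
|---|---|---|
| Last dose, shortest course | 2 + 10 − 1 = Day 11 | 2 + 33 − 1 = Day 34 |
| Last dose, nominal | 2 + 12 − 1 = Day 13 | 2 + 35 − 1 = Day 36 |
| Last dose, longest course | 2 + 14 − 1 = Day 15 | 2 + 37 − 1 = Day 38 |
| Last dose + 30 | Day 41 to 45 | Day 64 to 68 |
| Fixed visit window | Day 40 to 44 | Day 63 to 67 |
| Minimum gap | 40 − 15 = 25 | 63 − 38 = 25 |
| Nominal gap | 42 − 13 = 29 | 65 − 36 = 29 |
| Maximum gap | 44 − 11 = 33 | 67 − 34 = 33 |

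**Combinations below 30 days.** Let v be the visit deviation and t the dosing-length deviation, each a whole number from −2 to +2, which gives 25 pairs. For either operation:

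- Day 2 start: gap = 29 + v − t. It is under 30 when v − t ≤ 0, which is 15 of 25 pairs. The shortfall is 1 to 5 days.
- Day 1 start: gap = 30 + v − t. It is under 30 when v − t < 0, which is 10 of 25 pairs. The shortfall is 1 to 4 days.

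These are counts of permitted combinations, not probabilities.

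**Sensitivity of the gap (minimum / nominal / maximum, days).**

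- Day 2 start, calendar-day count: 25 / 29 / 33.
- Day 1 start, or last dose taken on the Day 12 ± 2 or Day 35 ± 2 visit: 26 / 30 / 34.
- Day 2 start, full elapsed days (last dose = first-dose day + length): 24 / 28 / 32.

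**Can both rules be met?** From a Day 2 start, last dose + 30 for TKR is Day 41, 42, 43, 44 or 45, against a window of Day 40 to 44. Four of the five dosing lengths fit, and the longest misses by one day. From a Day 1 start it is Day 40 to 44, and all five fit. THR behaves identically.

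**Early stopping.** Section 3.4.2 keeps the fixed days. After a single Day 2 dose, the nominal gap is 42 − 2 = 40 days (TKR) or 65 − 2 = 63 days (THR).

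**The case against.** The strongest defence reads the two synopsis sentences together: hold the visit 30 days after last dose, within the fixed window. That is feasible for four of five dosing lengths from Day 2 and for all five from Day 1, so the unavoidable shortfall is one day in one corner. This stands, and it rules out the inference that the two rules can never both be satisfied. It also rules out saying that a 25-day visit involves no protocol deviation: such a visit complies with 3.1.4 and the tables but conflicts with the synopsis sentence on 30 days. What the defence does not remove is that the places a site schedules from show only the fixed days.

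The 25-day figure also depends on convention. It needs a last dose on Day 15, one day after the latest Day 12 ± 2 visit. If the last dose falls on that visit, the nominal gap is exactly 30. The compliance formula in SAP 7.4.1 provides for a first dose on the day of surgery, which gives the same result. The minimum is therefore best given as 24 to 26 days. Under every convention some permitted combinations fall short.

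Reporting duties do not stop at the visit. SAEs must be collected for 30 days regardless (6.1.1), subjects are asked to report AEs during follow-up (3.1.4), and discharge instructions stress reporting bleeding in that period (5.3). So missed events are possible but not demonstrated. What is missing is a scheduled prompt for the last few days. For nonserious AEs the cover is thinner, since 6.2.1 gives a start of collection but no end.

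**Conclusion.** The point holds as a limited inconsistency. The fixed-day rule, followed alone, does not deliver the stated 30 days. With a Day 2 first dose and a calendar-day count, the nominal gap is 29 days and the permitted range is 25 to 33. Up to 5 days (4 to 6 across the conventions checked) can fall after the last scheduled contact and depend on unsolicited reports.

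Two larger inferences are not supported. The 15 of 25 and 10 of 25 counts do not estimate the share of subjects affected, because the documents give no distribution of dosing length or visit timing, and no number of missed events follows. Nor are the main results touched: the primary bleeding and secondary VTE/death endpoints stop at end of treatment + 2 days (synopsis; protocol 8.2 and 8.3; SAP 4.1 and 4.2). Only the descriptive AE/SAE summaries for the follow-up period are exposed. The mismatch also runs the other way, since subjects who stop well before the planned end are followed for more than 30 days on the fixed schedule.

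**What to change.** Reconcile the synopsis, protocol 3.1, 3.1.4, 3.4.2, Tables 5.1-1 and 5.1-2, protocol 6.1.1 and SAP 6.1 so that the visit and the 30-day window share one anchor. Which visit schedule is right is for the sponsor to settle.

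As a data-capture matter only, have the closing AE/SAE query cover the full stated 30-day window from each subject's actual last dose. This can be done at the visit or by the telephone contact the protocol already allows. Add to the SAP a count, by surgery type, of subjects whose last contact precedes the end of that window, so that readers can judge the completeness of the follow-up summaries.

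The cost is wording changes, and some closing contacts move by up to about 5 days.

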2 ETHICAL CONSIDERATIONS

2.1 Good Clinical Practice

This study will be conducted in accordance with Good Clinical Practice (GCP), as defined by the International Conference on Harmonisation (ICH) and in accordance with the ethical principles underlying European Union Directive 2001/20/EC and the United States Code of Federal Regulations, Title 21, Part 50 (21CFR50).

The study will be conducted in compliance with the protocol. The protocol and any amendments and the subject informed consent will receive Institutional Review Board/Independent Ethics Committee (IRB/IEC) approval/favorable opinion prior to initiation of the study.

All potential serious breaches must be reported to BMS immediately. A serious breach is a breach of the conditions and principles of GCP in connection with the study or the protocol, which is likely to affect, to a significant degree, the safety or physical or mental integrity of the subjects of the study or the scientific value of the study.

Study personnel involved in conducting this study will be qualified by education, training, and experience to perform their respective task(s).

This study will not use the services of study personnel where sanctions have been invoked or where there has been scientific misconduct or fraud (eg, loss of medical licensure, debarment).

